6.4 Capacity of Participants to Give Informed Consent

No vulnerable populations (e.g. children, cognitively impaired individuals, incarcerated individuals, or pregnant women) will be included in the study, and informed consent must be obtained directly from the participants.

7.0 STUDY DESIGN/METHODS

7.1 Study Overview

This is an open label trial of ketamine-assisted psychotherapy to assess the efficacy and safety of weekly intramuscular injections of ketamine along with multimodal psychotherapy, including supportive, non-directive and insight-oriented components, for decreasing symptoms of MDD in subjects with OUD in early or sustained remission. Psychotherapy will include setting goals for treatment of subject's depression as well as setting an intention or focus for each medication session. After medication administration, therapy will include supportive talk and guidance during acute medication effects. At the end of each session, the subject will be encouraged to reflect on his or her experience as it relates to their intention and broader goals. Finally, the subject will be encouraged to build insight into their depression and develop behavioral goals to enact their insights and reach their goals.

Subjects will participate in a baseline visit to complete informed consent as well as complete assessments to evaluate study eligibility and collect baseline data. Eligible participants will return for the initial ketamine intervention procedure. Participants will be subsequently monitored until they have returned to baseline based on clinical assessment during which time they will complete measures assessing their perception of the interventional experience

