4.0 STUDY ENDPOINTS

4.1 Primary Outcome

Montgomery Asberg Depression Rating Scale (MADRS; (Montgomery & Asberg, 1979)). The MADRS is a clinician administered, 10-item questionnaire of depression severity. The total score ranges from 0-60, with scores of 0-6 considered normal (non-depressed), 7-19 indicative of mild depression, 20-34 indicative of moderate depression, and 35-60 indicative of severe depression. Individuals scoring 20 or higher on the MADRS will be included in the study. The MADRS evaluates the following symptoms of depression: 1) clinical appearance of sadness, 2) self-reported sadness, 3) inner tension, 4) reduced sleep, 5) reduced appetite, 6) concentration difficulties, 7) lassitude, 8) inability to feel, 9) pessimistic thought process, and 10) thoughts of suicide. The MADRS has a sensitivity of 94% and a specificity of 83%, has been shown to have high internal consistency, and correlates well with other measures of depression such as the Hamilton Depression Scale.

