5.2 Inclusion Criteria

A subject may be eligible for enrollment if all the following inclusion criteria apply within the thirty days prior to first experimental session:

1. Between the ages of 18 to 64 years old.
2. Able to provide informed consent.
3. Meet DSM-5 criteria for Major Depressive Disorder, without psychotic features based on clinical interview.
4. Score at least 20 on the Montgomery-Asberg Depression Rating Scale (MADRS, moderate or severe depression).
5. Must meet criteria for opioid use disorder in early or sustained remission (3 months or great) by DSM-5 based on clinical interview.
6. Subjects taking other psychotropic medications (e.g. anti-depressants, anxiolytics, methadone, buprenorphine, naltrexone) must be maintained on a stable dose for at least four weeks before study initiation.

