7.3 Schedule of Assessments

The instruments to be used are standardized, have good psychometric properties, and are widely used. The schedule of study assessments is provided in **Table 1**.

Table 1: Schedule of Assessments

Instrument Name	Purpose	TIME POINT		
		BL (Wk 0)	Tx 1-8 (Wk 1-8)	Follow-up (Wk 9, 10, 12, 16)
Self-Reports and Consents				
Informed Consent	Obtain informed consent	X		
Demographics Form	Sample characterization	X		
Beck Depression Inventory-II	Self-reported assessment of depression symptom severity	X	X	X
Visual Analog Scale (VAS)	Measure subjective levels of opioid craving	X	X	X
General Anxiety Disorder (GAD-7)	Self-report of anxiety symptom severity	X	X	X
Mystical Experiences Questionnaire (MEQ)	Measure of perceptual experiences		X	
Brief Pain Inventory	Measure of pain and quality of life	X	X	X
Insomnia Severity Index (ISI)	Assess insomnia and sleep quality	X	X	X
Five Facets of Mindfulness (FFMQ)	Assess aspects of mindfulness related	X	X	X
PTSD Checklist (PCL-5)	Measure of PTSD symptoms	X	X	X
Fagerstrom Test of Nicotine Dependence (FTND)	Measure of nicotine dependence	X	X	X
Timeline Follow-Back (TLFB)	Measure of substance use	X	X	X
Clinician Assessments				
History and Physical Exam	Eligibility assessment	X		
Vital Signs Measurement	Obtain readings of blood pressure, pulse, temperature, respirations and pulse oximetry	X	X*	
Montgomery-Asberg Depression Rating Scale (MADRS)	Primary Outcome: Clinician assessed measure of depression symptom severity	X	X	X
Pre-screening Questionnaire	To assess for basic eligibility criteria before completing a full baseline visit.	X		
Laboratory and Procedural Tests				
Urine Pregnancy Test (female subjects only)	Eligibility assessment	X	X	
Urine Drug Screen	Assessment of illicit drug use	X	X	
Electrocardiogram (ECG; subjects on methadone only)	Assessment of cardiac function	X		

* Vital signs (blood pressure, pulse, respiratory rate, and pulse oximetry) will be obtained prior to treatment sessions and at 60 minutes post-treatment. Temperature will be monitored immediately prior to treatment. If there is an increase in systolic or diastolic blood pressure >30 mm Hg from baseline, or an increase in pulse rate >30 bpm from baseline, subjects will be treated with standard of care antihypertensive medications (i.e. clonidine) and the measurements will be repeated every 20 minutes until BP and pulse are within 30 points of the baseline values.

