7.4 Baseline Assessment Procedures

After completing study informed consent, participants will undergo a comprehensive evaluation to assess for inclusion and exclusion criteria. This will include self-reports and clinician assessments as shown in Table 1. This will also include assessment of depression severity and participants at highest risk for suicidality based on clinician assessment, those with a self-reported suicide attempt within the past year, and those felt likely to require hospitalization during the course of the study will be excluded. The comprehensive exam will also include a history and physical exam by the study PI (pulse oximetry measurements will be a component of the respiratory evaluation) and baseline medication evaluation for potential harmful interactions. Urine pregnancy tests will be completed for every woman of childbearing potential. Urine drug screening will be collected at baseline and prior to each ketamine session to monitor

for opioid and other illicit substance use. For patients currently taking methadone, ECG will be performed to assess for cardiac function with QTc interval of 450ms or longer being exclusionary. Assessments may be conducted by telehealth with vital signs to be provided by participant's home or pharmacy measurement.

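### The only MADRS labelled baseline is also the score that admits patients at 20 or more; used as the reference for change in this one-arm trial, it would count some regression to the mean as improvement

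*Combined protocol and SAP*

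**What the plan says.** Section 7.1 describes the design: "This is an open label trial of ketamine-assisted psychotherapy". There is one treatment and no comparison arm. Section 5.4 plans about 10 participants.

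The MADRS is the primary outcome; Table 1 in 7.3 labels it "Primary Outcome: Clinician assessed measure of depression symptom severity". It is also an entry test. Section 4.1 states "Individuals scoring 20 or higher on the MADRS will be included in the study", and 5.2 repeats the threshold: "Score at least 20 on the Montgomery-Asberg Depression Rating Scale".

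One visit does both jobs. Section 7.1: "Subjects will participate in a baseline visit to complete informed consent as well as complete assessments to evaluate study eligibility and collect baseline data". Section 7.4 describes the eligibility work-up as "a comprehensive evaluation to assess for inclusion and exclusion criteria. This will include self-reports and clinician assessments as shown in Table 1", and the MADRS is among those clinician assessments. Table 1 has one baseline column, Week 0.

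The first dose comes later. Section 7.1: "Eligible participants will return for the initial ketamine intervention procedure". Table 1 marks the MADRS at baseline, at treatment visits 1 to 8 and at follow-up. Section 7.5 places clinical assessments before drug administration, without naming the MADRS.

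Section 8.1 plans descriptive statistics to characterise participants. It gives no definition of MADRS change, no reference visit and no time point.

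**The concern.** Aim 1 (section 1.4) explores efficacy in reducing depression on the MADRS. Whoever fills the gap in 8.1 will most naturally take the score labelled baseline as the starting point, and that score has been truncated from below at 20. Selection of this kind favours patients whose rating was raised that day by measurement error or a temporary symptom peak. Unless scores at different visits correlate perfectly, the admitted group's mean then falls at later visits even if nothing is done, provided the mean of the candidate population is otherwise stable. In a controlled trial both arms would share the fall; here it would be credited to ketamine-assisted psychotherapy. A confidence interval for mean change does not reveal it, because the whole interval is shifted.

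**Working it through.** **Nothing to reproduce.** The plan gives no MADRS SD, no reliability, no expected change and no derivation of the sample size.

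**Inputs from the documents.** Entry cut-off 20 (4.1, 5.2); n = 10 (5.4); one arm (7.1).

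**Assumed inputs.** Candidate scores normal with mean 24 and SD 8; candidate mean stable without treatment; correlation r between the baseline score and a later score from 0.5 to 0.9.

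**Step 1: effect of selection.** a = (20 − 24)/8 = −0.5. L = φ(a)/(1 − Φ(a)) = 0.3521/0.6915 = 0.509. The admitted group's mean exceeds the candidate mean by SD × L = 8 × 0.509 = 4.07 points, so it is about 28.1.

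**Step 2: expected fall with no treatment effect.** Bias = (1 − r) × 4.07.

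**Step 3: comparison with sampling error.** The variance of admitted baseline scores is 64 × (1 + aL − L²) = 64 × 0.486 = 31.1. Untreated SD of change = √[(1 − r)² × 31.1 + 64 × (1 − r²)]. The 95% half-width is 2.262 × SD of change/√10.

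| r | Bias (points) | SD of change | 95% half-width | Bias/half-width |
|---|---|---|---|---|
| 0.9 | 0.41 | 3.53 | 2.5 | 16% |
| 0.8 | 0.81 | 4.93 | 3.5 | 23% |
| 0.7 | 1.22 | 5.95 | 4.3 | 29% |
| 0.6 | 1.63 | 6.78 | 4.8 | 34% |
| 0.5 | 2.04 | 7.47 | 5.3 | 38% |

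Over a wider assumed grid (mean 18 to 30, SD 6 to 10, r 0.5 to 0.9) the bias runs from 0.06 to 4.65 points; with a mean of 24 or more it runs from 0.06 to 2.81. Low candidate means look less likely, since 5.2 also requires patients to "Meet DSM-5 criteria for Major Depressive Disorder, without psychotic features based on clinical interview". That is an inference, not a figure in the protocol.

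**Step 4: what a Tx 1 reference would remove.** Remaining bias = (r between baseline and Tx 1 − r between baseline and the later visit) × 4.07.

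| r, baseline to Tx 1 | r, baseline to later | Bias from baseline | Bias from Tx 1 | Removed |
|---|---|---|---|---|
| 0.7 | 0.7 | 1.22 | 0.00 | 100% |
| 0.7 | 0.6 | 1.63 | 0.41 | 75% |
| 0.7 | 0.5 | 2.04 | 0.81 | 60% |
| 0.9 | 0.7 | 1.22 | 0.81 | 33% |
| 0.9 | 0.6 | 1.63 | 1.22 | 25% |
| 0.9 | 0.5 | 2.04 | 1.63 | 20% |

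Simulation of the first three rows (2 million draws) gave 1.23, 1.63 and 2.03 points from baseline and 0.00, 0.41 and 0.81 from Tx 1. A separate simulation with rounded scores and slowly drifting mood (variance shares 0.50 stable, 0.35 drifting, 0.15 error) gave 1.85 falling to 0.88 at a weekly correlation of 0.7 for the drifting part, and 1.39 falling to 0.68 at 0.9. About half is removed.

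**Step 5: precision.** At a stable r of 0.7, the SD of change from Tx 1 is 8 × √(2 × 0.3) = 6.20, so the half-width is 2.262 × 6.20/√10 = 4.43, against 4.26 from baseline. About 16% of admitted patients would score below 20 at Tx 1 untreated.

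**Step 6: visit count.** Table 1 implies 1 baseline + 8 treatment + 4 follow-up = 13 visits. Section 7.2 states 12.

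**The case against.** Five points can be made against this.

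- **The plan has not chosen the baseline score as its reference.** A reader might infer from the label that it has. The documents do not say so; 8.1 is silent. The point is therefore conditional. It still stands, because no other reference is named and the natural way to fill the gap is the biased one.
- **Rated before the injection does not mean untreated.** A reader might infer from 7.5 that the Tx 1 MADRS is a clean untreated score. Section 7.5 does not name the MADRS, and the treatment includes psychotherapy: 7.1 has goals and an intention set for sessions, apparently ahead of dosing. If that work precedes the rating, a Tx 1 reference would remove some treatment effect along with the regression. This objection stands, and the fix must specify the order. The shared treatment column in Table 1 does not settle timing, since it also holds a questionnaire about the drug experience.
- **The size is assumed and may be small.** Correct. At correlations of 0.8 and 0.9 the example gives only 0.8 and 0.4 points.
- **Tx 1 may remove little.** Also correct: with a baseline-to-Tx 1 correlation of 0.9 it removes 0.4 points, which is 20% to 33% of the bias in the scenarios shown.
- **The study is small and exploratory, and both scores will be collected anyway.** True, and this limits the importance. But choosing the reference after seeing both changes invites selection, and sampling error is symmetric while this bias is not.

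**Conclusion.** The point holds as a modest, conditional one. The documents establish that the only MADRS labelled baseline is the qualifying score, that there is no control arm, that no reference for change is named, and that a MADRS at the first treatment visit is already scheduled. If change is taken from the labelled baseline, part of it is regression to the mean.

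The size cannot be estimated from the documents. With the assumed mean of 24 and SD of 8 it is about 0.4 to 2.0 MADRS points for correlations from 0.9 to 0.5, which is 16% to 38% of the 95% half-width at n = 10. The direction does not depend on those values: in expectation it favours treatment whenever the correlation is below 1 and the candidate mean is otherwise stable.

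A reader might go further and infer that an observed improvement would be mostly artefact, or that a Tx 1 reference makes the estimate unbiased. The documents support neither. Expectancy, unblinded rating and natural recovery remain whichever reference is used.

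**What to change.** In 4.1 and 8.1:

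1. Use the baseline (Week 0) MADRS for eligibility.
2. State that the Tx 1 MADRS in Table 1 is rated before any of that session's psychotherapy and before the injection.
3. Use that score as the reference for MADRS change. Keep participants who score below 20 at Tx 1 in the analysis, because excluding them would select on the new reference.
4. Report change from the Week 0 score alongside it.

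This takes a few lines of text and a fixed order of procedures at Tx 1. It adds no rating, and no visit on the reading of 7.1 and Table 1 that Tx 1 is separate from baseline; the visit count in 7.2 should be reconciled with that reading. The reported improvement may be slightly smaller. Precision is nearly unchanged.

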7.2 Duration of Intervention and Study

Participants will complete a total of 12 study visits (including baseline assessment and follow-up assessments) as shown in **Figure 1**. Medication sessions with intramuscular ketamine will occur weekly for eight weeks. Participants will meet virtually or in person for follow-up 1, 2, 4, and 8 weeks following final medication session.

7.3 Schedule of Assessments

The instruments to be used are standardized, have good psychometric properties, and are widely used. The schedule of study assessments is provided in **Table 1**.

Table 1: Schedule of Assessments

Instrument Name	Purpose	TIME POINT		
		BL (Wk 0)	Tx 1-8 (Wk 1-8)	Follow-up (Wk 9, 10, 12, 16)
Self-Reports and Consents				
Informed Consent	Obtain informed consent	X		
Demographics Form	Sample characterization	X		
Beck Depression Inventory-II	Self-reported assessment of depression symptom severity	X	X	X
Visual Analog Scale (VAS)	Measure subjective levels of opioid craving	X	X	X
General Anxiety Disorder (GAD-7)	Self-report of anxiety symptom severity	X	X	X
Mystical Experiences Questionnaire (MEQ)	Measure of perceptual experiences		X	
Brief Pain Inventory	Measure of pain and quality of life	X	X	X
Insomnia Severity Index (ISI)	Assess insomnia and sleep quality	X	X	X
Five Facets of Mindfulness (FFMQ)	Assess aspects of mindfulness related	X	X	X
PTSD Checklist (PCL-5)	Measure of PTSD symptoms	X	X	X
Fagerstrom Test of Nicotine Dependence (FTND)	Measure of nicotine dependence	X	X	X
Timeline Follow-Back (TLFB)	Measure of substance use	X	X	X
Clinician Assessments				
History and Physical Exam	Eligibility assessment	X		
Vital Signs Measurement	Obtain readings of blood pressure, pulse, temperature, respirations and pulse oximetry	X	X*	
Montgomery-Asberg Depression Rating Scale (MADRS)	Primary Outcome: Clinician assessed measure of depression symptom severity	X	X	X
Pre-screening Questionnaire	To assess for basic eligibility criteria before completing a full baseline visit.	X		
Laboratory and Procedural Tests				
Urine Pregnancy Test (female subjects only)	Eligibility assessment	X	X	
Urine Drug Screen	Assessment of illicit drug use	X	X	
Electrocardiogram (ECG; subjects on methadone only)	Assessment of cardiac function	X		

* Vital signs (blood pressure, pulse, respiratory rate, and pulse oximetry) will be obtained prior to treatment sessions and at 60 minutes post-treatment. Temperature will be monitored immediately prior to treatment. If there is an increase in systolic or diastolic blood pressure >30 mm Hg from baseline, or an increase in pulse rate >30 bpm from baseline, subjects will be treated with standard of care antihypertensive medications (i.e. clonidine) and the measurements will be repeated every 20 minutes until BP and pulse are within 30 points of the baseline values.

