5.3 Exclusion Criteria

Subjects will be excluded from the study if any of the following criteria apply:

1. They are considered an immediate suicide risk by clinician assessment, self-report a suicide attempt within the past year or felt to be likely to require hospitalization during the study.
2. Subjects who meet DSM-5 criteria for current bipolar disorder based on clinical interview.
3. Subjects who meet DSM-5 criteria for current or history of psychotic spectrum disorders based on clinical interview.
4. Subjects meeting DSM-5 criteria for current substance use disorder (*i.e.*, not in early or sustained remission) other than tobacco use disorder.
5. Subjects who report use of ketamine >20 times in the past or who meet DSM-5 criteria for Other Hallucinogen Use Disorder due to ketamine use including subjects who are currently in early or sustained remission.
6. Women who are pregnant or nursing, and women who do not consent to use methods of highly effective birth control during the interventional phase of the study.
7. Subjects with hypertension as defined by a baseline visit systolic blood pressure (SBP) >140 mmHg or a diastolic blood pressure (DBP) >90 mmHg.
8. A history of allergic or other adverse reaction to ketamine (or its excipients).
9. Clinically significant physical exam findings or self-reported medical conditions for which a transient increase in blood pressure could be significantly detrimental (e.g. glaucoma, aneurysmal disease, cardiovascular disease, or end-stage renal disease).
10. QTc will be measured in subjects currently taking methadone and those with QTc 450ms or longer will be excluded.
11. Subjects who live greater than 20 miles from the study site and cannot arrange their own transportation will be excluded from the study.
12. Subjects with clinically significant kidney or liver impairment.

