7.5 Intervention Visit Procedures

Prior to administration of the study compounds, participants will complete self-report questionnaires and clinical assessments. The study physician will disinfect the subject's shoulder using an alcohol wipe, and the study physician will then administer the medication by intramuscular administration into the participant's deltoid muscle. Vital signs will be monitored prior to treatment, and at 60 minutes post-treatment. If during the post-administration observation period, ketamine administration causes an increase in systolic or diastolic blood pressure >30 mm Hg from baseline, or an increase in pulse rate >30 bpm from baseline, the subject will be treated with standard of care antihypertensives (i.e. clonidine), and repeat vital sign measurements will be taken approximately every 20 minutes until blood pressure and pulse are within 30 points of baseline values. Standard of care antihypertensive medications will be procured via intrainstitutional transfer from MUSC investigational drug services pharmacy distribution center. They will be stored in a DHEC compliant locked box within a locked room accessible only to study team members. If the subject experiences symptoms of hypertensive emergency, the subject will not receive further administration of ketamine and will be withdrawn from the study. After completion of the injection, participants until returned to baseline per clinical assessment which time they will undergo debriefing and complete assessments of their perceptual experience of the intervention. We will evaluate the effects of a weekly interventions for 8 sessions. Participants will return for follow-up assessment 1, 2, 4 and 8 weeks following final medication session. Follow-up visits may be conducted by telehealth.

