11.2 Physical Risks

The most significant physical adverse event from ketamine is a transient increase in blood pressure, which in previous studies was experienced by 29.8% of subjects with a mean systolic blood pressure increase of 19.6 mmHg +/- 12.8 mmHg and a mean diastolic blood pressure increase of 13.4 mmHg +/- 9.8 mmHg. Peak levels are reached on average 40 minutes post-treatment and resolve by 240 minutes post-treatment (Wan et al., 2015). Participants experiencing clinically significant hypertension (greater than 180 mmHg SBP or greater than 105 mmHg DBP, or greater than 30 mmHg SBP or DBP from baseline values) will be treated with standard of care hypertensives (e.g. clonidine) and monitored until symptom resolution.

The most prevalent physical adverse effect was transient sedation and occurs in approximately 16% of patients receiving ketamine. Sedation will be monitored via continuous clinical observation during interventional sessions. A medical emergency team will be called for participants that are unable to be aroused with painful trapezius squeeze or that experience hypoxia (i.e. a pulse oximeter reading of 92% or less), although in the investigative team's extensive experience using ketamine clinically for depression at these doses, such serious events have never occurred. Vital signs will be routinely monitored during treatment and emergency airway equipment will be immediately available. Subjects will be monitored for 2 hours post-dose by trained healthcare professionals (eg PI, co-I, or study nurse). Due to transient cognitive impairment associated with sedation, participants will not be allowed to drive themselves following the interventions. Subjects who do not have transportation and live within 20 miles will receive compensation for taxi, Uber or Lyft transportation to and from medication sessions up to \$100 each way. Subjects who live greater than 20 miles from the study site and cannot arrange their own transportation will be excluded from the study. Participants will be advised not to operate heavy machinery for at least 24 hours after the interventions.

There are also the standard risks associated with intramuscular injections including temporary local pain, irritation, or redness at the site of the injection. There is a very small (<1%) risk of infection, muscle fibrosis, or persistent muscle or nerve damage at the site of injection.

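### The visit procedures (7.3, 7.5) state a narrower post-dose blood pressure rule than section 11.2, so some diastolic readings above 105 mm Hg are treated under one section and not acted on under the others

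*Combined protocol and SAP*

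**What the plan says.** Three sections of the combined protocol and SAP say what to do about a pressure rise after ketamine.

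- **7.3, Table 1 footnote.** Treatment and repeat readings every 20 minutes start "If there is an increase in systolic or diastolic blood pressure >30 mm Hg from baseline" or on a pulse rise above 30 bpm. Repeats continue "until BP and pulse are within 30 points of the baseline values".
- **7.5, Intervention Visit Procedures.** The trigger is that "ketamine administration causes an increase in systolic or diastolic blood pressure >30 mm Hg from baseline", or the same pulse rise. Repeats are taken about every 20 minutes "until blood pressure and pulse are within 30 points of baseline values". The scheduled readings are few: "Vital signs will be monitored prior to treatment, and at 60 minutes post-treatment".
- **11.2, Physical Risks.** Clinically significant hypertension is "greater than 180 mmHg SBP or greater than 105 mmHg DBP, or greater than 30 mmHg SBP or DBP from baseline values". Subjects who meet it "will be treated with standard of care hypertensives (e.g. clonidine) and monitored until symptom resolution". This section gives no repeat interval and no pulse limit.

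Section 5.3 bounds the entry pressure by excluding a "baseline visit systolic blood pressure (SBP) >140 mmHg or a diastolic blood pressure (DBP) >90 mmHg". A subject can therefore enter with a diastolic of up to 90 and a systolic of up to 140. The protocol does not say whether the baseline in these rules is the Week 0 visit or the reading before each injection, and it sets no pressure limit on the pre-dose reading.

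**The concern.** The absolute limits of 180 and 105 appear only in the risk section. The sections that describe what happens at each of the eight medication sessions have only the relative limit of 30. For a subject whose diastolic starts fairly high, a reading above 105 can fall short of a 30-point rise. Someone working from 7.3 or 7.5 then has no instruction to treat or re-measure a pressure that 11.2 calls clinically significant and says to treat.

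The end of follow-up has the same gap. Even if 11.2 prompts treatment, the only numeric rule for ending repeat readings is the within-30 rule. In this band that rule is satisfied before any drug is given, so no timed reading after clonidine is required. Section 11.2 ends monitoring at symptom resolution, and a raised pressure need not cause symptoms.

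Section 11.2 names the transient pressure rise as the most significant physical adverse event of the drug, so this rule should read the same wherever it appears.

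**Working it through.** The plan has no figure of its own to reproduce here. The check compares the rules and then gauges how often they would differ.

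**1. Where the triggers differ.** Let *b* be the reference diastolic and *p* the post-dose diastolic, in whole mm Hg.

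- Visit rule (7.3, 7.5): act if *p* − *b* > 30.
- 11.2 rule: act if *p* > 105 or *p* − *b* > 30.

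They differ when 105 < *p* ≤ *b* + 30, which needs *b* > 75. For whole numbers that is *b* ≥ 76, with discordant readings from 106 to *b* + 30:

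| Reference diastolic | Discordant post-dose diastolic |
|---|---|
| 75 or less | none |
| 76 | 106 only |
| 80 | 106 to 110 |
| 85 | 106 to 115 |
| 90 | 106 to 120 |

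The top row of 90 is a ceiling only if baseline means the Week 0 visit, where 5.3 caps diastolic at 90. If it means the pre-dose reading, the band continues upward. In either case the visit procedures must not already have been triggered by a systolic or pulse rise above 30.

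**2. Systolic.** At the Week 0 cap, 140 + 30 = 170, below 180, so there is no gap. A systolic gap needs a reference of 151 or more (151 + 30 = 181). That is possible only if baseline means the pre-dose reading.

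**3. Example (assumed readings, pulse rise 30 or less).** Pre-dose 125/88, at 60 minutes 148/112.

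- Rises: 148 − 125 = 23 and 112 − 88 = 24. Neither exceeds 30, so 7.3 and 7.5 do not act.
- 112 > 105, so 11.2 treats.
- The end point under 7.3 and 7.5 is 88 + 30 = 118. At 112 it is already met.

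**4. Frequency (illustration).** Inputs from 11.2: mean systolic rise 19.6 (SD 12.8), mean diastolic rise 13.4 (SD 9.8). Assumptions: normal rises, correlation between 0 and 0.8, pulse trigger ignored because the protocol gives no pulse data. The quantity is P(diastolic > 105, and neither rise > 30).

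With zero correlation it is a product. P(systolic rise ≤ 30) = Φ((30 − 19.6)/12.8) = Φ(0.81) = 0.792. P(diastolic rise ≤ 30) = Φ((30 − 13.4)/9.8) = Φ(1.69) = 0.955. At reference 80, P(diastolic rise ≤ 25) = Φ((25 − 13.4)/9.8) = Φ(1.18) = 0.882. The result is 0.792 × (0.955 − 0.882) = 0.058. The other cells use the bivariate normal distribution.

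| Reference | Correlation 0 | 0.5 | 0.8 | Range × 0.298 |
|---|---|---|---|---|
| 80 | 0.058 | 0.040 | 0.022 | 0.007 to 0.017 |
| 85 | 0.163 | 0.127 | 0.096 | 0.029 to 0.049 |
| 90 | 0.309 | 0.268 | 0.241 | 0.072 to 0.092 |

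The last column applies if the means in 11.2 describe only the 29.8% of subjects who had a rise, which its wording allows and may favour. Taking both readings together, the range is about 0.7 to 6% of doses at reference 80 and 7 to 31% at 90.

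**The case against.** The strongest reply is that nothing here is a contradiction. Sections 7.3 and 7.5 say when to treat and do not forbid treatment otherwise. Section 11.2 contains the same 30-point trigger plus two more, so staff can comply with all three sections by following 11.2. Follow-up is not absent either. Section 11.2 has vital signs monitored routinely during treatment and two hours of post-dose observation by trained staff. Section 9.0 requires continuous monitoring until return to medical and psychiatric baseline, which on its face is stricter than being within 30 points. A physician gives each injection.

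Most of this stands, and it limits the stake. Read together, the sections settle whether to treat. They do not settle when repeat readings may stop. None of the wider monitoring provisions gives a pressure or an interval, and the one rule that does is already met in this band.

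A reader might infer more than the text supports in three ways:

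- **That the sections disagree for every subject with a reference diastolic of 76 to 90.** They disagree only for readings in the band, with systolic and pulse rises of 30 or less. At 76 the band is a single value, and 90 is an upper limit only under the Week 0 reading of baseline.
- **That the tolerability results under Aim 2 would depend on which section staff followed.** The protocol defines no count of treated hypertensive events. Section 8.4 records any event judged to be adverse, whether or not it was treated.
- **That up to 31% of doses would be affected.** That figure is for a subject exactly at a reference of 90, with unscaled means and zero correlation. The protocol gives no distribution of reference pressures.

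**Conclusion.** The point holds as an internal inconsistency in a safety rule. For a reference diastolic of 76 or more, a post-dose diastolic from 106 to the reference plus 30, and no systolic or pulse rise above 30, section 11.2 requires treatment while 7.3 and 7.5 require neither treatment nor a repeat reading. This follows from the text and needs no distributional assumption.

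The frequency does need such assumptions and should be read as a rough range only. It rests on normal rises, an assumed correlation and a fixed reference. The source figures come from intravenous studies in which pressure peaked at about 40 minutes, whereas this trial injects intramuscularly and schedules its reading at 60 minutes, so the rate seen then may be lower. The consequence is modest given the other monitoring. The documents do not support a claim that subjects go unobserved or that the efficacy or adverse event results would be distorted. The correction is still worth making, because following the visit procedures as written falls short of a limit that the protocol itself sets.

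**What to change.** In 7.3 and 7.5:

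- add to the trigger: *or systolic BP >180 or diastolic BP >105*;
- add to the end of repeats: *and BP no longer exceeds 180/105*.

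In 11.2, replace the separate instruction with a reference to that rule, including its pulse trigger and 20-minute interval. Symptom resolution can stay as an additional condition.

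In the example above, the subject at 112 would then be treated and re-measured every 20 minutes until diastolic was 105 or less, where the present end point is 118.

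As a separate clarification, state which reading baseline means. The same-session pre-dose value is a reasonable choice and is already taken at every session.

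The cost is a sentence or less in each of three places. The limits and the interval are already in the protocol. Some subjects would have a few extra readings within the existing two-hour observation.
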